2.6.2.5 Handling of missing values/censoring/discontinuations

Patients will be censored for the secondary endpoints according to the same method described in section 2.5.2.1 and 2.5.2.2.

2.6.3 Safety analyses

The safety and tolerability assessments are:

- a. Physical examination;
- b. Vital signs (sitting systolic and diastolic blood pressure, and pulse);
- c. Pregnancy assessment;
- d. Electrocardiogram;
- e. Adverse events;
- f. Serious adverse events;
- g. Adverse events of special interest:
 - Arrhythmia
 - Angioedema
 - Symptomatic hypotension
 - Hyperkalemia
 - Renal dysfunction

For all safety analyses, the SAF will be used. All listings and tables will be presented by treatment arm.

Safety summaries (tables, figures) include only data from the on-treatment period with the exception of baseline data which will also be summarized where appropriate (e.g., change from baseline summaries). In addition, a separate summary for death including on treatment and post treatment deaths will be provided. In

particular, summary tables for the Adverse Events (AEs) will summarize only on-treatment events, with a start date during the on-treatment period (treatment-emergent AEs).

The on-treatment period lasts from the date of first administration of study treatment to 30 days after the date of the last actual administration of any study treatment.

2.6.3.1 Vital signs

All vital signs (Pulse [beats/min], BMI [kg/m²], Supine systolic blood pressure [mmHg] and Supine diastolic blood pressure [mmHg])) data will be listed by treatment arm, subject, and visit/time and if ranges are available, abnormalities (Pulse below 50 bpm and above 120 bpm; Systolic Blood Pressure below 90 mmHg and above 180 mmHg; Diastolic Blood Pressure below 50 mmHg or above 105 mmHg) will be flagged. Summary statistics will be provided by treatment and visit/time and as change from baseline.

2.6.3.2 Twelve-lead ECG

All ECG data (Rhythm, P-wave duration, Heart rate, QRS Complex Duration, QT Interval, will be listed by treatment arm, subject and visit (Baseline and EOS), abnormalities (Pathological Q Waves, Left anterior fascicular block, Posterior fascicular block, Complete Left Bundle Branch Block, Right Bundle Branch Block, Left Ventricular Hypertrophy, Low QRS voltage) will be flagged. Summary statistics will be provided by treatment at V1 and EOS.

2.6.3.3 Adverse events

All information obtained on AEs will be displayed by treatment arm and listed by subject.

The treatment emergent adverse events (events started on or after the first dose of study medication or events present prior to the first dose of study medication but increased in severity based on preferred term on or after the first dose of study

medication until 30 days after study's treatment last dose) will be summarized by primary System Organ Class (SOC) and Preferred Term (PT).

Separate summaries will be provided for study medication-related AEs, death, SAEs, other significant AEs leading to discontinuation.

2.6.3.4 Adverse events of special interest

The number (and proportion) of participants with AEs of special interest, AESI (i.e., angioedema, arrhythmia, symptomatic hypotension, hyperkalemia, and renal dysfunction), will be summarized by treatment.

In order to identify any potential AESI a search query was applied on each category of pre-defined AEs. The search strategy is outlined in Table 4. The search query uses much broader list of terms, as well as additional clinically relevant terms that may represent AESI like events. All identified AEs were followed up with the site for further assessment and to confirm if they fulfil the criteria of AESI. Each AESIs had their own CRF form to be completed by the Investigator with detailed information.

Table 4. Adverse Events of Special Interest search strategy.

AESI	Search methodology
Angioedema	SMQ (narrow) Angioedema, and additional PTs Anaphylactic reaction, Anaphylactic shock, Anaphylactoid reaction, Anaphylactoid shock, Auricular swelling, Bronchial oedema, Endotracheal intubation, Gastrointestinal oedema, Genital swelling, Laryngeal dyspnea, Laryngeal obstruction, Laryngospasm, Ocular hyperemia, Oedema peripheral (only LLTs Edema extremity upper, Edema upper extremities, Edema upper limb, Oedema extremity upper, Oedema upper extremities, Oedema upper limb, Upper limb edema, Upper limb oedema), Oedema genital, Orbital oedema, Oropharyngeal spasm, Penile oedema, Penile swelling, Reversible airways obstruction, Scrotal oedema, Scrotal swelling, Skin oedema, Stridor, Throat tightness, Tracheal obstruction, Upper airway obstruction, Vaginal oedema, Visceral oedema, Vulval oedema, Vulvovaginal swelling.
Arrhythmia ¹	
Hyperkalemia	'Blood potassium abnormal', 'Blood potassium increased' and 'Hyperkalemia'
Symptomatic hypotension	Altered state of consciousness', 'Blood pressure abnormal', 'Blood pressure ambulatory abnormal', 'Blood pressure ambulatory decreased', 'Blood pressure decreased', 'Blood pressure diastolic abnormal', 'Blood pressure diastolic decreased', 'Blood pressure fluctuation', 'Blood pressure immeasurable', 'Blood pressure inadequately controlled', 'Blood pressure orthostatic abnormal', 'Blood pressure orthostatic decreased', 'Blood pressure systolic abnormal', 'Blood pressure systolic decreased', 'Blood pressure systolic inspiratory decreased', 'CT hypotension complex', 'Consciousness fluctuating', 'Depressed level of consciousness', 'Dialysis hypotension', 'Diastolic hypotension', 'Dizziness', 'Dizziness exertional', 'Dizziness postural', 'Hypotension', 'Hypotensive crisis', 'Labile blood pressure', 'Loss of consciousness', 'Mean arterial pressure decreased', 'Neonatal hypotension', 'Orthostatic hypotension', 'Post procedural hypotension', 'Presyncope', 'Procedural hypotension', 'Schellong test', 'Syncope', and 'Tilt table test positive'

AESI		Search methodology
Renal dysfunction	SMQ (narrow)	Acute renal failure
(1) In the event that a clinically significant ECG abnormality is identified at the study site (e.g., severe arrhythmia, conduction abnormality, or QTcF > 500 ms), a copy of the assessment is to be sent to the local laboratory for expedited review if applicable, and the ECG is repeated to confirm the diagnosis. If the participant is hemodynamically compromised, the Investigator or a medically qualified person must initiate appropriate safety procedures without delay (for example cardioversion). Clinically significant abnormalities must be recorded on the eCRF as either medical history/current medical conditions or AEs as appropriate.		

The incidences of AESI will be compared between arms using Fisher's Exact Test as an exploratory evaluation, since the trial was not designed or powered for those comparisons.

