## **6.4 Treatment blinding**

Treatment will not be blinded to participants, Investigator staff, and persons performing the assessments. However, treatment will be blinded to the clinical trial team to avoid any bias during the study. Blinding of the DMC and the Clinical Endpoint Adjudication Committee are described in separate documents as outlined in [Section 10.2.2](#) and [Section 10.2.3](#).

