## 16.3 Appendix 3: Specific renal alert criteria and actions and event follow up

**Table 16-3 Specific renal alert criteria and actions**

Renal Event	Actions
Confirmed serum creatinine increase 25 – 49%	
 
Consider causes and possible interventions
 
Follow up within 2-5 days
 

Serum creatinine increase $\geq 50\%$ * OR if <18 years old, eGFR <math>\leq 35</math> mL/min/1.73 m^2	
 
Consider causes and possible interventions
 
Repeat assessment within 24-48h if possible
 
Consider drug interruption or discontinuation unless other causes are diagnosed and corrected
 
Consider patient hospitalization and specialized treatment
 

New onset dipstick proteinuria $\geq 3+$ OR Protein-creatinine ratio (PCR) $\geq 1\text{g/g Cr}$ (or mg/mmol equivalent as converted by the measuring laboratory)	
 
Consider causes and possible interventions
 
Assess serum albumin & serum total protein
 
Repeat assessment to confirm
 
Consider drug interruption or discontinuation unless other causes are diagnosed and corrected
 

New onset hematuria $\geq 3+$ on urine dipstick	
Assess & document
 
 
Repeat assessment to confirm
 
Distinguish hemoglobinuria from hematuria
 
Urine sediment microscopy
 
Assess sCr
 
Exclude infection, trauma, bleeding from the distal urinary tract/bladder, menstruation
 
Consider bleeding disorder
 

\* Corresponds to KDIGO criteria for Acute Kidney Injury

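### AESI tables: sites that know the treatment confirm the search hits, the SAP does not say which count is analysed, and the renal search is one narrow query with no added terms

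*SAP*

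**What the plan says.** SAP 2.6.3.4 plans a by-arm summary of participants with each of five AESIs: angioedema, arrhythmia, symptomatic hypotension, hyperkalemia and renal dysfunction. It describes three steps.

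- **Search:** "In order to identify any potential AESI a search query was applied on each category of pre-defined AEs". The section adds that "The search query uses much broader list of terms", together with further clinically relevant terms.
- **Site follow-up:** "All identified AEs were followed up with the site for further assessment and to confirm if they fulfil the criteria of AESI".
- **Form:** the investigator completes a dedicated AESI form.

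Incidences are then compared between arms with Fisher's exact test, labelled exploratory. The section does not say which of these steps supplies the count.

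In SAP Table 4 the renal dysfunction row is the narrow standardised query (SMQ) "Acute renal failure" and nothing else.

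On blinding, Protocol 6.4 states: "Treatment will not be blinded to participants, Investigator staff, and persons performing the assessments". Protocol 10.2.3 describes blinded adjudication for the primary endpoint. SAP 2.6.3.4 mentions only the sites.

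**The concern.** **Confirmation.** Whether a search hit fulfils the AESI criteria is decided by people who know the drug, against criteria that neither document states as AESI criteria. Those people also have arm-specific expectations. Protocol 4.5.1 gives them, for sacubitril/valsartan against enalapril, hypotension 17.61% v 11.97%, renal dysfunction 10.14% v 11.52% and angioedema 0.5% v 0.2%. If the confirmation rate differs by arm, the AESI ratio moves even when the true rates are equal. No laboratory data can expose this, because values other than NT-proBNP are used only locally to trigger adverse events (Protocol 8.4.1, SAP 2.6.4).

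**Renal row.** The protocol's renal concern is creatinine rise and eGFR fall (Protocol 6.5). Its alert table starts at "Confirmed serum creatinine increase" of 25 to 49% (Table 16-3). A row limited to a narrow acute-failure query may not gather such events when they are reported as adverse events.

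Comparative safety is secondary objective 6 in Protocol Table 2-1, and AESIs are a named part of it.

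**Working it through.** **1. The Table 4 rows side by side**

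| Row | Search as written |
|---|---|
| Angioedema | narrow SMQ plus a long list of added preferred terms |
| Hyperkalemia | named terms, including abnormal and increased blood potassium |
| Symptomatic hypotension | long list, including decreased blood pressure, dizziness and syncope |
| Renal dysfunction | narrow acute renal failure SMQ only |
| Arrhythmia | no terms legible in the text available, only a footnote; nothing is concluded from this |

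Renal dysfunction is the only populated row limited to a narrow SMQ with no added terms, although the section describes a broader list.

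**2. Inputs for an illustration.** The plan gives no target rate or power for AESIs, so there is no figure of its own to reproduce. The earlier HFrEF trial's renal rates in Protocol Table 4-1 do reproduce: 426/4203 = 10.14% and 487/4229 = 11.52%. Arm size is the target of 450; the safety set may be smaller. Query sensitivity and confirmation rates are **assumptions**, since the documents give none. Fisher's test is taken as two-sided at 0.05, also an assumption, and evaluated by exact enumeration.

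Formula: counted rate = true rate × query sensitivity × confirmation probability. The true rate is set to 11.52% in both arms, so expected participants are 450 × 487/4229 = 51.8 per arm.

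**3. The query alone, applied equally to both arms**

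- Sensitivity 0.8, 0.6 or 0.4 leaves 41.5, 31.1 or 20.7 per arm.
- The ratio stays 1.00, and the chance of a significant Fisher test stays at 3.5 to 3.9%.
- Precision falls. SE of the log risk ratio = sqrt[2 × (1/x − 1/450)], with x participants per arm:
  - x = 51.8: sqrt[2 × (0.01930 − 0.00222)] = 0.185
  - 25% lost, x = 38.9: sqrt[2 × (0.02573 − 0.00222)] = 0.217, which is 17% larger
  - 50% lost, x = 25.9: sqrt[2 × (0.03859 − 0.00222)] = 0.270, which is 46% larger

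**4. Confirmation that differs by arm (no true difference)**

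| Confirmed, arm A v arm B | Apparent ratio | P(Fisher < 0.05), sensitivity 1.0 | Same, sensitivity 0.4 |
|---|---|---|---|
| 100% v 100% | 1.00 | 3.9% | 3.5% |
| 90% v 70% | 0.90/0.70 = 1.29 | 18.9% | 8.4% |
| 80% v 60% | 0.80/0.60 = 1.33 | 20.7% | 9.0% |
| 70% v 90% | 0.70/0.90 = 0.78 | 18.9% | 8.4% |

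The two mechanisms act differently. The renal query lowers counts and precision. Only confirmation (or reporting) that differs by arm moves the ratio, and it can move it either way.

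**The case against.** - **The counting rule.** A reader might infer that an AESI counts only after passing both the search and the site, so that a creatinine event is lost unless the SMQ holds it. The SAP does not say so. The search can also be read as a sweep for missed cases alongside AESIs that investigators file on their own form; it would then add cases. This stands, and the rule is open.
- **Search hits as an unbiased count.** A reader might take search-positive events as arm-neutral. The term list is, but the events searched are not. Under Protocol 10.1.1 unblinded investigators identify adverse events, and a laboratory abnormality qualifies only if it causes symptoms, is judged clinically significant or needs therapy. This stands.
- **SMQ contents.** The documents do not list them, so omission of particular renal terms is possible but not shown. The evidence is internal: the row's difference from the other rows and from the protocol's renal focus.
- **Renal harm remains visible.** SAP 2.6.3.3 tabulates treatment-emergent events by SOC and preferred term, with separate summaries for SAEs and for events leading to discontinuation. Reported creatinine or eGFR events are not lost. They are only split across terms, without a participant-level renal total.
- **Criteria.** The documents are not silent on thresholds: Appendix 4 starts hyperkalemia guidance above 5.3 mmol/L, and Table 8-2 defines notable hypotension. Neither is labelled an AESI criterion. Table 16-3 prescribes site actions, and its only eGFR alert is for participants under 18, who are not eligible.
- **Blinded review.** Protocol 4.1 extends blinded evaluation to events that could meet secondary endpoints, and Table 2-1 lists AESIs under secondary endpoint 6. But 10.2.3 names only the primary endpoint, and SAP 2.6.3.4 gives the committee no role.
- **Low stakes.** The tests are exploratory. At the Table 4-1 renal rates (about 46 v 52 participants) Fisher's test has only about 8% power. This limits the importance but does not remove the ambiguity.

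**Conclusion.** The point holds in a limited form. SAP 2.6.3.4 has search hits confirmed by sites that know the treatment, with no stated AESI criteria and no blinded review, and leaves open which count is analysed. Arm-aware confirmation could skew the AESI comparison. Under the assumed 90% v 70% confirmation, the ratio is 1.29 (0.78 if reversed) and the false-positive rate about 19% with full query sensitivity. The documents fix neither the size nor the direction, and do not show that confirmation did differ.

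The renal row is out of line with the section's own description and with the protocol's renal focus. If it misses 25 to 50% of renal participants (assumed), the SE of the log risk ratio is 17 to 46% larger. That is a loss of precision and of a pooled renal count. It does not mean that renal harm disappears from the report, or that the renal ratio is biased by the query. Label: cheap improvement.

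**What to change.** In SAP 2.6.3.4:

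1. Report, by arm, participants with a search-positive AE (fixed Table 4 terms) beside participants with a site-confirmed AESI. Give the Fisher comparison for both, and the proportion of search-positive participants confirmed in each arm. Labelled columns settle what is counted, and the confirmation proportions expose any difference between arms.
2. Add reported-AE terms for creatinine increased and eGFR decreased to the renal row, plus any non-acute renal impairment terms that the narrow SMQ does not already hold.

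**Cost:** re-running a term search on adverse events already coded, with no new site contact. **Downside:** search-positive counts are less specific (dizziness is in the hypotension list) and still rest on open-label AE reporting. They should therefore sit beside the confirmed counts rather than replace them, with a note saying so.

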##### 4.5.1 Risks

Experience from 4203 patients treated with sacubitril/valsartan and 4229 patients treated with enalapril in the PARADIGM-HF study indicate that the major risks associated with both treatments are renal dysfunction, hyperkalemia, and hypotension ([Table 4-1](#)).

**Table 4-1** Rate of events per treatment during the Follow-up Period of the PARADIGM-HF study

Event	Sacubitril/valsartan (n = 4203)	Enalapril (n = 4229)
	n (%)	n (%)
Renal dysfunction	426 (10.14)	487 (11.52)
Hyperkalemia	488 (11.61)	592 (14.0)
Hypotension	740 (17.61)	506 (11.97)

n: number of participants

Results from the TITRATION study indicate that more participants who were naïve to previous ACEI or ARB therapy or on low doses of these agents were able to achieve and maintain sacubitril/valsartan 200 mg when up-titrated slowly (over 6 weeks).

In this study, the risk of renal dysfunction and hypotension will be mitigated by appropriate slow up-titration of the study drugs. Participants with CCC are at higher risk of hypotension because of the early involvement of both ventricles. Therefore, the titration will be slow to

decrease the risk of hypotension. The risks will be further mitigated by appropriate application of the exclusion criteria. Participants will be excluded if they have an eGFR < 30 mL/min/1.73 m^2.

Drug-to-drug interactions are known to occur with the concomitant use of ACEs, ARBs, neutral endopeptidases, and renin inhibitors. Participants will be provided with study drug instructions and their prior and concomitant medication use will be reviewed at Screening and at all subsequent visits.

Confirmed cases of angioedema were observed in the randomized treatment epoch of PARADIGM-HF, with both sacubitril/valsartan (19 [0.5%] of 4203 participants) and enalapril (10 [0.2%] of 4229 participants). The risk of developing angioedema is increased in participants who take an ACEI in addition to sacubitril/valsartan. To decrease this risk, participants using ACEIs will be required to undergo a 36-hour washout before they start sacubitril/valsartan to minimize the potential drug interaction.

The study procedures and assessments are either non-invasive or minimally invasive (venipuncture for blood draws) and are considered to pose low risk.

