### **5 Population**

The study participants will consist of men and women aged 18 years or older with NYHA Class II-IV HFrEF (LVEF ≤ 40%) caused by Chagas' disease. The target projected sample size is approximately 900 participants (450 in each arm). It is estimated that approximately 1800 participants will be screened at up to approximately 100 study sites because a screen failure rate of approximately 50% is anticipated, based on previous experience in other HF studies.

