### 6.1.3 Treatment arms

Participants eligible for Randomization at Visit 101 will be assigned to one of the following treatment arms in a 1:1 ratio:

- sacubitril/valsartan 200 mg BID
- enalapril 10 mg BID

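### The SAP compares adverse events of special interest between arms by an exploratory Fisher test on crude incidences, with no effect estimate, confidence interval or exposure-adjusted rate

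*SAP*

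**What the plan says.** SAP 2.6.3.4 summarises "The number (and proportion) of participants with AEs of special interest" by treatment. It then plans a formal test of the arms against each other on these proportions, described as a Fisher's "Exact Test as an exploratory evaluation, since the trial was not designed or powered for those comparisons". The five AESIs are angioedema, arrhythmia, symptomatic hypotension, hyperkalemia and renal dysfunction.

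The rest of the safety output in SAP 2.6.3 (treatment-emergent and serious events, deaths, vital signs, ECG) is descriptive by arm. Under SAP 2.6.4, laboratory values other than NT-proBNP are not entered in the eCRF. SAP 2.6.3 limits adverse event tables to the period from first dose to 30 days after last dose. Protocol 6.4 leaves treatment unblinded to participants and site staff.

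Protocol 12.5.2 plans a summary of AESIs and no test. The test enters in the SAP and is not listed among the changes in SAP section 3.

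For background rates, Protocol 4.5.1 says that data from an earlier large heart failure trial of the same two drugs "indicate that the major risks associated with both treatments are renal dysfunction, hyperkalemia, and hypotension". It gives counts for these three events in Table 4-1 and for angioedema in the text below it.

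**The concern.** Objective 6 (Protocol Table 2-1, SAP Table 1) is comparative. A bare p-value from a test known to have little power does not say which differences the data exclude. An interval does.

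The plan also treats AESIs less fully than comparable endpoints:

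- SAP 2.1 says data will be analysed with stratification by country. Fisher's test has no strata.
- SAP 2.6.2.2 (emergency room visits) and SAP 2.8 (treated sustained ventricular tachycardia) use a negative binomial model with a follow-up offset and report a ratio with a 95% CI. The tachycardia endpoint is itself exploratory, so that label does not explain the missing estimate for AESIs.
- Because events count only on treatment plus 30 days, time at risk stops soon after discontinuation. If discontinuation differs between open-label arms, a crude proportion mixes event risk with time on drug.

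At stake is how well the trial answers a stated secondary objective. No efficacy result is affected.

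**Working it through.** **Inputs.** Protocol section 5: "The target projected sample size is approximately 900 participants (450 in each arm"); allocation 1:1 (Protocol 6.1.3). The Safety Set size is not stated, so 450 per arm is assumed and 400 to 460 is shown as a range. No level or sidedness is given for the Fisher test; two-sided 5% is assumed. Event rates are from Protocol 4.5.1, sacubitril/valsartan v enalapril:

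- renal dysfunction 426/4203 = 10.14% v 487/4229 = 11.52%
- hyperkalemia 488/4203 = 11.61% v 592/4229 = 14.00%
- hypotension 740/4203 = 17.61% v 506/4229 = 11.97%
- angioedema 19/4203 = 0.45% v 10/4229 = 0.24%

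No rate is given for arrhythmia.

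**The plan's own figure.** The documents state no power for any AESI, so the design figure of 302 participants with events was reproduced instead. With exponential times and follow-up uniform on 1.5 to 3 years, P(λ) = 1 − [exp(−1.5λ) − exp(−3λ)]/(1.5λ). This gives P(0.20) = 0.360 and P(0.16) = 0.301, so expected events = 450 × (0.3600 + 0.3006) = 297.3, which is 1.6% below 302. The reading of sample size and follow-up is therefore sound. Planned mean follow-up is (18 + 36)/2 = 27 months, against a median of 27 months in the source trial (Protocol 1.1), so its crude rates are on a similar time scale.

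**Power of the Fisher test.** For every pair of counts (x, y), the two binomial probabilities were multiplied, and the products were summed over pairs with Fisher p ≤ 0.05. Non-significance is one minus that sum.

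| AESI | Power, 450 per arm | Non-significant, 450 per arm | Non-significant, 400 to 460 per arm |
|---|---|---|---|
| Hyperkalemia | 16.2% | 83.8% | 85.3 to 83.4% |
| Renal dysfunction | 8.3% | 91.7% | 92.2 to 91.5% |
| Angioedema | 0.7% | 99.3% | 99.6 to 99.3% |
| Hypotension | 63.2% | 36.8% | 42.1 to 35.6% |

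**Sensitivity to the borrowed rates.** Replacing each risk p by 1 − (1 − p)^f, with f from 0.5 to 2, moves non-significance over 91 to 72% (hyperkalemia), 94 to 87% (renal), 100 to 96% (angioedema) and 64 to 11% (hypotension).

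**What an estimate would show.** At the expected proportions, the risk difference is d ± 1.96 × √[p₁(1 − p₁)/450 + p₂(1 − p₂)/450]. For hyperkalemia, d = 0.1161 − 0.1400 = −0.0239 and SE = √(0.1161 × 0.8839/450 + 0.1400 × 0.8600/450) = 0.0223, giving −2.4 points (−6.8 to 2.0). The same formula gives:

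- renal dysfunction: −1.4 (−5.4 to 2.7)
- hypotension: +5.6 (1.0 to 10.3)

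For angioedema the expected counts are 450 × 0.0045 = 2.0 and 450 × 0.0024 = 1.1. A result of 2 v 1 gives Fisher p = 1.0, while its Newcombe interval is −0.9 to +1.4 points. The test needs 6 v 0 (p = 0.031); 5 v 0 gives p = 0.062.

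**The case against.** The strongest reply is that the SAP already calls the test exploratory and unpowered. That stands: the low power is disclosed and is not in itself an error.

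Several stronger readings are tempting, and the documents do not support them.

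- *The safety conclusion will rest on non-significance.* No section makes the test a decision rule or plans a conclusion of no difference. Counts and proportions are reported, so a reader could work out a crude interval.
- *The test would hide harms of sacubitril/valsartan.* In Protocol 4.5.1 the hyperkalemia and renal differences favour that drug. Of the two that go against it, angioedema would almost never reach significance, but hypotension would in about 63% of trials.
- *No safety-related outcome gets an estimate.* All-cause mortality and sudden death or resuscitated arrest get hazard ratios with intervals (SAP 2.6.2.1), and treated sustained ventricular tachycardia gets a rate ratio (SAP 2.8). These are classed as efficacy or exploratory endpoints, so the point is confined to the safety section.

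The borrowed rates also deserve caution. This trial's AESIs are symptomatic hypotension and renal dysfunction found by a narrow acute renal failure search and then checked with the site, whereas Table 4-1 simply lists hypotension and renal dysfunction. Protocol 4.5.1 also expects more hypotension in Chagas' cardiomyopathy.

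What remains is that none of this supplies an estimate, an interval or an exposure-adjusted rate for the AESIs.

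**Conclusion.** The point holds as a low-cost improvement to the safety reporting. The SAP safety section offers one formal comparison, an unstratified exact test on crude incidences, and specifies no measure of how large a difference is or how precisely it is known. The non-significance figures (84%, 92%, 99% and 37%) rest on 450 per arm, a two-sided 5% level and rates carried over from another trial with different event definitions. They show how little the p-value would say for three AESIs, and that hypotension is an exception. Country stratification is probably the smallest part; the missing interval and person-time rate are the main ones. How far time on treatment will differ between arms is not known from the documents.

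**What to change.** In SAP 2.6.3.4, for each of the five AESIs:

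1. Report a risk difference with 95% CI in place of, or alongside, the exploratory p-value. Use Mantel-Haenszel weighting by country, and unstratified exact or score limits when there are fewer than 5 events per arm. About 3 angioedema cases are expected in total, over the four countries named in SAP Appendix 4.1, so stratification would not be workable there.
2. Report first-event incidence per 100 patient-years with a rate ratio and 95% CI. Time at risk runs from first dose to the first event or 30 days after last dose, to match the on-treatment window.

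The cost is deriving that time-at-risk variable and adding a few table columns. The exposure days in SAP 2.4.1 are a starting point but not sufficient, because they sum dosing intervals by dose level and do not include the 30-day tail. The person-time rate reduces the effect of differential or informative discontinuation but does not remove it, and the text should say so. List the AESI comparison in SAP section 3 as a change from the protocol.
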